7.1.3 Steroid refractory GVHD

The first salvage therapy for patients who are not responding to itacitinib is systemic steroid treatment. Patients treated with systemic steroids whose GVHD worsens (increase by one or more grade) after 3 days, **or** fails to respond to treatment within 7 days (for GVHD grade III) **or** 14 days (for GVHD grade II) **or** who start additional lines of therapy beyond systemic steroid treatment within 28 days of starting steroids will be considered steroid refractory. Escalation of steroid doses during treatment for GVHD are not considered in the definition of steroid refractory GVHD.

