2.3 Primary Endpoint

Proportion of patients who achieve CR or PR by day 28 of treatment with itacitinib without the addition of any other systemic GVHD treatment including steroids.

CR is defined as absence of GVHD symptoms. PR is defined as improvement in one or more organs involved with GVHD symptoms without progression in other organs. For a response to be scored as CR or PR on day 28, the patient must be in CR or PR on day 28 and have had no intervening systemic therapy for acute GVHD other than itacitinib.

Secondary endpoints:

- Cumulative incidence of steroid-refractory GVHD (defined as GVHD that worsens (increase by one or more grade) after 3 days, or fails to respond to treatment within 7 days (for GVHD grade III) or 14 days (for GVHD grade II) or 2nd line therapy beyond systemic steroid treatment is begun within 28 days of starting steroids.
- 2. Distribution of maximal GVHD grade (I-IV) by day 28 after starting treatment with itacitinib
- 3. Cumulative incidence of serious infections (defined as bacteremia, CMV infection needing treatment, EBV infection needing treatment, or invasive fungal infection)
- 4. Overall survival at 6 and 12 months
- 5. Cumulative incidence of NRM at 6 and 12 months
- 6. Relapse rate at 6 and 12 months
- 7. Cumulative incidence of chronic GVHD requiring systemic steroid treatment by one year from enrollment

8. Cumulative steroid dose (over 4 weeks) in patients who receive steroids as second line therapy

Safety endpoints

1. Number and proportion of patients developing reportable AEs and SAEs according to relatedness to study drug and stratified by severity

Exploratory endpoints

1. GVHD biomarker concentrations (ST2 and REG3) and their associations with clinical endpoints at day 28 after starting treatment with itacitinib

The two hypotheses are: 1) that GVHD biomarkers will remain low in study patients who respond to itacitinib treatment, but will rise in non-responders and (2) biomarker concentrations will be equivalent to those in historical control patients who respond to steroid treatment for low risk GVHD.

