5.1.7 GVHD treatment

The preliminary data for this study were generated from patients transplanted at multiple centers with heterogeneous GVHD treatment practices. In order to develop "real world" experience in this study, institutional GVHD treatment practices are permitted unless their use is explicitly prohibited.

Systemic steroid treatment should be started if any of the following criteria are met: GVHD worsens (increase by one or more grade) after 3 days, or failure to respond to treatment within 7 days (for GVHD grade III) or 14 days (for GVHD grade II). The decision to remove a patient from study treatment should be discussed with the site PI. Itacitinib must be stopped when systemic steroid treatment is begun. When systemic steroid treatment is initiated, the minimum starting dose is prednisone (or other steroid form equivalent) 1 mg/kg/day for GVHD that involves only the skin and/or upper GI tract and 2 mg/kg/d for GVHD that involves the lower GI tract and/or liver. Institutional practices can be followed for steroid tapering schedules.

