7.0 GVHD CLINICAL STAGING

GVHD clinical staging will be according to the established criteria used for MAGIC clinical trials.

	Stage 0	Stage 1	Stage 2	Stage 3	Stage 4
Skin	No rash	Rash < 25% BSA	25-50%	> 50% Generalized erythroderma	Plus bullae and desquamation >5% BSA
Liver	Bilirubin ≤ 2 mg/dl	2.1-3 mg/dl	3.1-6mg/dl	6.1-15mg/dl	>15mg/dl
GI tract	Adult: < 500 ml/day Children <10 mg/kg/d	Adult: 500–1000 ml/day Children 10-19.9 mg/kg/d	Adult: 1001-1500 ml/day Children 20- 30 mg/kg/d	Adult: >1500 ml/day Children > 30 mg/kg/d	Severe abdominal pain +/- ileus, frank blood or melena (regardless of stool volume)
UGI		Severe nausea/vomiting			

• For GI GVHD, children is defined as <18 years of age and <50 kg weight

• For stage 4 GI GVHD, severe abdominal pain is defined as (1) pain that requires opioid use **and** (2) pain that significantly impacts on performance status as determined by the treating physician

• Comprehensive GVHD staging guidance is provided in the MAGIC GVHD Staging Guidance.

Overall Clinical Grade:

Grade 0	No stage 1-4 of any organ
Grade I	Stage 1-2 skin and no liver or GI involvement
Grade II	Stage 3 skin and/or Stage 1 liver and/or Stage 1 GI
Grade III	Stage 0-3 skin with Stage 2-3 liver and/or Stage 2-3 GI
Grade IV	Stage 4 in any target organ (skin, liver, GI)

Minnesota Risk Scoring⁶:

Standard Risk:

Stage 1-3 skin (single organ system)
Stage 1-2 GI (single organ system)
Stage 1-3 skin + Stage 1 GI (two organ system involvement)
Stage 1-3 skin + Stage 1-4 liver (two organ system involvement)
High Risk: Any other combination of single or dual organ aGVHD stages

Minnesota risk scoring calculator: http://z.umn.edu/MNAcuteGVHDRiskScore

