8.7 Stopping Rules

We will monitor the study subjects for both efficacy and toxicity. We will allow continuous accrual on to the study unless a stopping rule is met or the target accrual is reached. The study may also be stopped based on the recommendation of the investigators, the TCI DSMC, or at Incyte's discretion for any reason.

Steroid-refractory GVHD:

We expect itacitinib monotherapy to be safe because of its extensive use in >700 patients prior to this trial. However, in order to protect study subjects we have designed three stopping rules that will terminate the trial early if itacitinib monotherapy as a treatment for GVHD is either too toxic or ineffective. First, our preliminary data show that the incidence of steroid-refractory GVHD using the definition in section 2.3 in the low risk population eligible for this trial is 38%. For an itacitinib monotherapy trial to be successful, the proportion of patients who develop steroid-refractory GVHD should not exceed 38%. We expect that patients who do not respond to itacitinib will be responsive to steroid treatment and we will continuously monitor the incidence of steroid-refractory GVHD in all study subjects. Patients will be considered to have steroid refractory GVHD if their GVHD is treated with systemic steroids and they either do not respond by day 28 of steroid treatment. The trial will be halted if the incidence of steroid-refractory GVHD is greater than the

associated boundary value b_k listed in the table below, among the k patients enrolled in the trial, then accrual will be halted.

Maximum # of Patients, k	5	6-8	9-10	11-13	14-16	17-19	20-22	23-25	26-28	29-31	32-35
Boundary, b _k	3	4	5	6	7	8	9	10	11	12	13
Maximum # of Patients, k	36-38	39-41	42-44	45-48	49-51	52-54	55-58	59-61	62-65	66-68	69-70
Boundary, b _k	14	15	16	17	18	19	20	21	22	23	24

Specifically, if more than 3 out of the first 5 patients, 4 out of the first 8 patients, 5 out of the first 10 patients, 6 out of the first 13 patients, or 24 out of the first 70 patients, experience steroid-refractory GVHD, the trial will be halted for safety considerations.

The operating characteristics of this stopping rule are as follows:

	True Steroid Refractory Rate 24% 30% 33% 0.38 40% 42%						
Probability of Early Stopping	0.10	0.36	0.54	0.83	0.88	0.94	

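### Steroid-refractory GVHD is defined in two different ways, and the definition behind the 38% benchmark has no non-response day for grade IV or grade I

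*Combined protocol and SAP*

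**What the plan says.** Section 7.1.3 gives three routes to steroid-refractory status once systemic steroids have begun:

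- worsening: patients "whose GVHD worsens (increase by one or more grade) after 3 days";
- non-response by a day that depends on grade: "fails to respond to treatment within 7 days (for GVHD grade III", with 14 days for grade II;
- a further line: patients "who start additional lines of therapy beyond systemic steroid treatment within 28 days of starting steroids will be considered steroid refractory".

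The secondary endpoint in section 2.3 has the same routes and the same two grades: "fails to respond to treatment within 7 days (for GVHD grade III) or 14 days (for GVHD grade II". The grading table in section 7.0 ends at grade IV, defined as "Stage 4 in any target organ (skin, liver, GI".

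The stopping rule in section 8.7 has its own sentence. It counts patients whose GVHD is "treated with systemic steroids and they either do not respond by day 28 of steroid treatment". The word *either* introduces an alternative that never follows. The same paragraph gives the benchmark: "the incidence of steroid-refractory GVHD using the definition in section 2.3 in the low risk population eligible for this trial is 38" percent.

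The treatment text in section 5.1.7, on when to move from itacitinib to steroids, names the same two grades: "failure to respond to treatment within 7 days (for GVHD grade III) or 14 days (for GVHD grade II".

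**The concern.** Under 2.3 and 7.1.3, a patient who is grade IV when steroids start cannot rise a grade and has no non-response day. If that patient stays at grade IV or dies on steroids alone, no event is scored. A grade I patient who never improves and never worsens is not scored either, unless a further line is added.

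Section 8.7 would count both patients as non-responders at day 28, but it compares its total with a rate tabulated under 2.3. One label therefore covers two events.

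This endpoint carries weight. Section 11.2 accepts the drop from 67% to 52% in response only if steroid-refractory GVHD does not increase. The endpoint also drives a stopping rule (8.7), is compared with historical controls (11.3), and feeds the decision on a phase III trial (11.2). Because 5.1.7 permits institutional treatment practice, whether a further drug is added, and so whether a grade IV failure registers under 2.3, can vary between sites and between the trial and the historical cohort.

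**Working it through.** **Step 1. Who is counted under each wording**

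| Patient after starting steroids | 2.3 / 7.1.3 | 8.7 as printed |
|---|---|---|
| Grade II or III at start, rises a grade after 3 days | event | event only if no response by day 28 |
| Grade III, no response by day 7, responds by day 28 | event | not an event |
| Grade IV at start, no response, further line within 28 days | event | event |
| Grade IV at start, no response, steroids alone | not an event | event |
| Grade IV at start, dies early on steroids alone | not an event | not stated; an event if death is read as no response |
| Grade I at start, no response, no rise, no further line | not an event | event |

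The wordings differ in both directions. Section 8.7 adds the grade IV and grade I non-responders. As printed, it drops early failures that recover by day 28. A count made under 8.7 could therefore sit above or below the 2.3 count in the same patients.

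**Step 2. If 2.3 is used for both the trial and the benchmark**

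The wording gap is then shared, but it need not cancel. Section 1.3 describes the low-risk cohort as newly diagnosed standard-risk patients treated with steroids. In the section 7.0 tables, the only standard-risk pattern that can be grade IV is skin disease with stage 4 liver, so few of that cohort would have started steroids at grade IV. Trial patients start steroids after failing itacitinib and could have reached grade IV by then. The grade I gap may work the other way: stage 1-2 skin disease is standard risk, whereas a trial patient moved to steroids because of a rise in grade is already above grade I. Neither share is given, so the net direction is not determined.

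**Step 3. The plan's own stopping figures**

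Inputs are the boundaries b_k in section 8.7 (from k = 5, b = 3, to k = 69-70, b = 24), with a stop when the count exceeds b_k. Let d_k(j) be the probability of j events among the first k patients with no stop so far:

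d_k(j) = (1 − p)·d_{k−1}(j) + p·d_{k−1}(j − 1)

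At each k, the mass with j > b_k is removed and added to the stopping probability.

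| True rate p | 24% | 30% | 33% | 38% | 40% | 42% |
|---|---|---|---|---|---|---|
| Section 8.7 | 0.10 | 0.36 | 0.54 | 0.83 | 0.88 | 0.94 |
| Recomputed | 0.100 | 0.361 | 0.548 | 0.819 | 0.890 | 0.939 |

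All agree to about one percentage point. Stopping at *b_k or more* does not reproduce the table (0.903 at 38%).

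**Step 4. Sensitivity to missed patients**

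Assume that monitoring uses 2.3, that the benchmark does not share the gap, and that m of 70 patients are missed. The observed rate is p − m/70, and 1/70 = 1.43 points. The documents give no value for m; 0 to 2 is an assumption.

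| m | True 38%: observed rate | Stop | True 33%: observed rate | Stop |
|---|---|---|---|---|
| 0 | 38.0% | 0.82 | 33.0% | 0.55 |
| 1 | 36.6% | 0.75 | 31.6% | 0.46 |
| 2 | 35.1% | 0.68 | 30.1% | 0.37 |

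The 33% columns are shown because section 11.2 gives the historical rate as 33%, where 8.7 and the synopsis give 38%; that discrepancy is a separate matter. The rule is sensitive because 0.38 × 70 = 26.6 expected events lie close to the 25 needed to cross the final boundary. If monitoring follows the 8.7 day-28 sentence, grade IV non-responders are counted, this gap removes no events, and these reductions do not apply.

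**The case against.** A reader might infer that the worst steroid failures are invisible to the stopping rule unless a clinician adds a drug, and that the monitored rate is therefore biased low. The documents do not support this. The day-28 sentence in 8.7 has no grade limit and, read as printed, covers grade IV. The 38% was obtained under 2.3, so if 2.3 governs monitoring as well, the benchmark has the same wording gap.

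The affected group is also narrow. A patient who starts steroids at grade II or III and rises to grade IV after 3 days is an event. Entry requires Minnesota standard risk, Ann Arbor 1 and, apart from Gilbert syndrome, direct bilirubin below 2 mg/dL, so grade IV at entry is largely excluded. Assessments are at least weekly during induction. A missed patient must reach grade IV before steroids start, fail them, and receive no further line within 28 days. Non-relapse deaths within 6 months also count under their own stopping rule.

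These points stand, and they remove any claim about the direction of bias. They do not remove the inconsistency. The 8.7 sentence is unfinished and differs from the definition behind its benchmark. Section 11.1 ties the reported endpoint to 2.3, which 8.7 does not alter. Counting a death under the mortality rule does not correct its classification in this endpoint.

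**Conclusion.** The point holds as a problem of definition, of minor severity. Under 2.3 and 7.1.3, the endpoint under-counts patients who are grade IV at steroid start and fail on steroids alone, and it leaves grade I non-response unscored. Section 8.7 counts a different event and compares it with a rate obtained under 2.3. How many patients are affected, and the net direction against 38%, cannot be determined from the documents.

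The fall in stopping probability from 0.82 to about 0.75 or 0.68 shows how sensitive the rule is. It does not estimate an actual bias, because it rests on three assumptions: monitoring by 2.3, a benchmark without the gap, and 1 or 2 patients missed. With none missed there is no effect.

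**What to change.** For endpoint scoring only:

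1. Reconcile 2.3, 7.1.3 and 8.7 into one definition whose non-response clause covers every grade at steroid start, including IV and I. The sponsor should choose the scoring days and state them in all three places.
2. State that death with active GVHD on steroids is scored as refractory.
3. Complete the 8.7 sentence to match, so that the monitoring count and the reported endpoint are the same event.
4. Re-tabulate the 38% from existing consortium data under that definition, and regenerate the boundaries if it moves.

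The cost is a wording change in three sections and one re-tabulation. The downside is a possible small change in the benchmark and hence in the boundaries. The treatment text in 5.1.7 also names only grades II and III for non-response; the sponsor must reconcile it, and no treatment rule is proposed here.

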7.1.4 Steroid discontinuation

For patients who initiate systemic steroid treatment for GVHD, the date of discontinuation of steroid therapy will be recorded.

7.1.5 Lines of GVHD therapy

The initiation of systemic steroids for treatment of GVHD will be considered second line therapy. Any additional systemic immunosuppression treatment to steroid therapy for acute GVHD will be considered 3rd line therapy and considered a failure to respond to steroid treatment. Resumption or changes in GVHD prophylaxis (e.g., substitution of mycophenolate for tacrolimus due to PRES) are not considered new lines of therapy. Topical steroids and non-absorbable oral steroids are not considered new lines of therapy.

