3.2 Exclusion Criteria

3.2.1 Patients currently being treated with any JAK inhibitor including ruxolitinib

- 3.2.2 Relapsed, progressing, or persistent malignancy requiring withdrawal of systemic immune suppression
- 3.2.3 Patients with uncontrolled infection (i.e., progressive symptoms related to infection despite treatment or persistently positive microbiological cultures despite treatment or any other evidence of severe sepsis)
- 3.2.4 Severe organ dysfunction including requirement for dialysis, mechanical ventilation, or oxygen supplementation exceeding 40% FiO2 within 7 days of enrollment.
- 3.2.5 Creatinine clearance or estimated glomerular filtration rate <30 ml/min as calculated by institutional practice (e.g., Cockcroft-Gault equation, CKD-EPI equation, etc)
- 3.2.6 A clinical presentation resembling de novo chronic GVHD or overlap syndrome developing before or present at the time of enrollment
- 3.2.7 Patients receiving corticosteroids >10 mg/day prednisone (or other steroid equivalent) for any indication within 7 days before the onset of acute GVHD except for adrenal insufficiency or premedication for transfusions/IV meds
- 3.2.8 Patients who are pregnant
- 3.2.9 Patients receiving investigational agents within 30 days of enrollment. However, the Principal Investigator (PI) may approve prior use of an investigational agent if the agent is not expected to interfere with the safety or the efficacy of itactinib
- 3.2.10 History of allergic reaction to itacitinib or any JAK inhibitor

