5.1.6 GVHD Prophylaxis Medications

Medications given for GVHD prophylaxis such as cyclosporine, tacrolimus, sirolimus, methotrexate, mycophenolate should be continued at therapeutic doses (according to institutional standards) and adjusted as necessary for renal, central nervous system (CNS) or other toxicity using institutional guidelines. This study allows for changes in GVHD prophylaxis medication (e.g., replacement of cyclosporine with sirolimus for management of posterior reversible encephalopathy syndrome [PRES]) as per institutional standards. GVHD prophylaxis medications will be tapered according to local institutional tapering practices.

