7.1 ENDPOINT AND RESPONSE CRITERIA

7.1.1 **Definitions**

Evaluable for response: Safety, tolerability, and efficacy of itacitinib will be assessed from the initiation of the first itacitinib treatment

Complete Response (CR): All evaluable organs (skin, liver, GI tract) stage 0. For a response to be scored as CR on day 28, the patient must be in CR on that day and have had no intervening additional GVHD therapy.

Partial Response (PR): An improvement in one or more organ involved with GVHD symptoms without worsening in others. For a response to be scored as PR on day

28, the patient must be in PR on that day and have had no intervening additional GVHD therapy.

No response (NR): All responses that are not CR or PR. Patients who receive any systemic GVHD therapy other than the continuation or modification of GVHD prophylaxis, systemic steroids, and topical/non-absorbable oral steroid therapy, will be scored as NR on day 28 regardless of organ staging.

7.1.2 **Proportion of CR and CR+PR**

CR and PR on day 28 are scored in comparison to the patient's acute GVHD staging on the day itacitinib treatment began.

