11.3 Data Analysis Plans

The primary endpoint is the proportion of patients who achieve CR or PR by day 28 of treatment with itacitinib without the addition of any other systemic GVHD treatment including steroids. Death, lack of GVHD response to itacitinib by day 28 of treatment, or initiation of steroid or other systemic immunosuppressive therapy for GVHD will be considered failures for this endpoint. The proportion of patients who achieve CR or PR by day 28 in the study patients will be compared to the historical control rate of 67%.

Secondary outcomes such as cumulative incidence of steroid-refractory GVHD, proportion of patients with maximal grade I, II, III, and IV GVHD by day 28 after starting treatment with itacitinib, cumulative incidence of serious infections, cumulative incidence of hematologic toxicities, cumulative steroid dose over four weeks in patients who fail itacitinib monotherapy, overall survival at 6 and 12 months, cumulative incidence of NRM at 6 and 12 months, relapse rate at 6 and 12 months, and cumulative incidence of chronic GVHD requiring systemic steroid treatment by one year will be estimated and compared to historical controls.

Continuous variables will be summarized using standard summary statistics such as number of observations (n), mean, standard deviation (SD), minimum and maximum values, median, and 1st and 3rd quartiles. Categorical variables will be summarized in frequency tables as counts and percentages.

Cumulative incidence of non-relapse mortality will be estimated by Gray's method⁵³ and relapse will be considered as a competing risk. Disease free and overall survival, defined as the time from the transplantation to death or to last follow-up if alive, will be estimated by the method of Kaplan-Meier and the probability curves and 95% confidence intervals will be provided based on the method of Brookmeyer and Crowley⁵⁴.

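### The non-response definition in section 7.1.1 exempts prophylaxis changes made for any reason (and, read literally, systemic steroids), so some co-treated patients can be scored as monotherapy responders against sections 2.3, 11.1 and 11.3

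*Combined protocol and SAP*

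**What the plan says.** The primary endpoint in section 2.3 is CR or PR on day 28. To count, the patient must "have had no intervening systemic therapy for acute GVHD other than itacitinib". Section 11.1 repeats this. Section 11.3 states the failure side: "initiation of steroid or other systemic immunosuppressive therapy for GVHD will be considered failures for this endpoint". None of the three mentions a prophylaxis exemption.

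Section 7.1.1 sets the response categories. Its CR and PR definitions also require that no further GVHD therapy was given in between. Its non-response definition then says who is forced into that category whatever the organ staging: "Patients who receive any systemic GVHD therapy other than the continuation or modification of GVHD prophylaxis, systemic steroids, and topical/non-absorbable oral steroid therapy". The items after the words *other than* are exempt, and no reason, timing or dose limit is attached to them.

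Section 7.1.5, which numbers lines of therapy, says "Resumption or changes in GVHD prophylaxis (e.g., substitution of mycophenolate for tacrolimus due to PRES) are not considered new lines of therapy". The sentence before it counts systemic immunosuppression added to steroids for acute GVHD as third line and as failure of steroids.

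Two provisions make the situation foreseeable. Section 5.1.6 states "This study allows for changes in GVHD prophylaxis medication" and leaves tapering to local practice. Section 5.1.7 states that "institutional GVHD treatment practices are permitted unless their use is explicitly prohibited". The notes to the Time and Events Table require immunosuppressants and GVHD drugs to be recorded, but give no rule for classifying them.

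**The concern.** The endpoint is meant to measure response to itacitinib alone. Take a patient whose tapered prophylaxis drug is restarted or increased in the first weeks because the GVHD is not settling, and who is in PR on day 28. The non-response sentence in 7.1.1 does not exclude this patient; 2.3 and 11.3 do. No section says when a prophylaxis drug used against active GVHD becomes therapy for GVHD, and none provides for review of that label. The central guidance and audits described in section 1.5 concern staging and grading.

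The trial is open-label with a single arm, so response to the added drug would be credited to itacitinib and compared with a fixed 52% bound. The exemption can only turn a failure into a success, so any error favours the non-inferiority claim.

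**Working it through.** **Scoring the same patient under each provision** (each assumed to have CR- or PR-level staging on day 28)

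| After day 0 the patient has | 7.1.1 non-response sentence | 2.3, 11.1, 11.3 | Agree? |
|---|---|---|---|
| Prophylaxis drug substituted for toxicity | Exempt | Not therapy for GVHD | Yes |
| Prophylaxis drug increased or resumed because GVHD is active | Exempt as a modification | Systemic therapy for GVHD: failure | No |
| Systemic steroid for GVHD | Exempt if read literally | Failure | No |
| Systemic steroid for another indication | Not GVHD therapy | Not GVHD therapy | Yes |

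Two details of wording matter. Resumption is named in 7.1.5 but not in 7.1.1, so exempting it in scoring depends on reading it as a modification. Section 11.3 refers to initiation, so a dose increase of a running drug conflicts more clearly with 2.3 than with 11.3.

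**Inputs for the size.** N = 70, expected response 67% and bound 52% (Synopsis and 11.2); one-sided exact test at 0.04 with 81% power (Synopsis); 80% power, stop at 19 or fewer of 35, final boundary 44 (11.2).

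**The plan's own figures.** For a single look, P(X ≥ r) with X ~ Bin(70, p):
- r = 44: power 0.807 at p = 0.67; type I error 0.044 at p = 0.52.
- r = 45: power 0.732; type I error 0.026.

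The stated 81% is reproduced with r = 44. With the interim look,

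P(claim) = Σ (a = 20 to 35) P(Bin(35, p) = a) × P(Bin(35, p) ≥ r − a).

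- r = 44: power 0.786; type I error 0.041.
- r = 45: power 0.719; type I error 0.025.

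The first is close to the stated 80%. Both values of r are carried forward because 11.2 prints 44 in a futility column and explains only the interim boundary, where reaching the number means stopping. Read the same way at the end, success would need 45.

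**Illustration.** Assume true monotherapy response is 52%, and that an expected m of 70 patients who would otherwise fail are scored as responders through the exemption. The scored rate is p = 0.52 + m/70.

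| m | p | P(claim), r = 44 | P(claim), r = 45 |
|---|---|---|---|
| 0 | 0.5200 | 0.041 | 0.025 |
| 1 | 0.5343 | 0.066 | 0.042 |
| 2 | 0.5486 | 0.103 | 0.068 |
| 3 | 0.5629 | 0.152 | 0.105 |

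An expected two such patients (2/70 = 2.9%) more than double the false-positive probability under either reading.

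**The case against.** The strongest reply is that the provisions mostly deal with different things. Section 7.1.5 numbers lines of therapy and scores no day-28 response. Sections 2.3 and 11.3 concern therapy for GVHD, and the CR and PR definitions in 7.1.1 agree with them. The only worked examples of a prophylaxis change, in 5.1.6 and 7.1.5, are toxicity cases. Sections 7.1.3 and 5.1.7 make systemic steroids the first salvage, with itacitinib stopped when they start, so the literal steroid exemption is probably a drafting slip. Most of this stands. It confines the problem to changes made in response to GVHD and to the 7.1.1 sentence. It does not remove the problem, because that sentence is part of the response definition and exempts modification without regard to reason.

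A reader might infer three stronger points that the documents do not support:

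- *That 7.1.5 itself makes the co-treated patient a responder.* It does not score response. It can touch the limb of the steroid-refractory definition in 7.1.3 that refers to additional lines. Even there, its preceding sentence already counts immunosuppression added for acute GVHD, and the other limbs of 7.1.3 do not depend on lines.
- *That 11.3 is inconsistent with eligibility criterion 3.2.7,* which excludes "Patients receiving corticosteroids >10 mg/day prednisone (or other steroid equivalent) for any indication within 7 days before the onset of acute GVHD", with listed exceptions. That is an entry screen for the period before onset; 11.3 is an outcome rule. Using the 10 mg threshold to score response would be a change of endpoint.
- *That the response rate will be inflated by a known amount.* The documents give no frequency of such changes. They also do not say whether the historical 67% was scored with the same exemption. If it was, part of the bias relative to that benchmark would cancel.

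**Conclusion.** The inconsistency is real and lies in the primary endpoint's scoring text. One sentence of 7.1.1 conflicts with the CR and PR definitions beside it and with 2.3, 11.1 and 11.3, for prophylaxis drugs changed because GVHD is active and, literally, for steroids. Its direction is certain; its size is not. The range of 0.066–0.152 (or 0.042–0.105) rests on an assumed one to three reclassified patients, a true rate exactly at the 52% bound, and each of those patients being a failure without the added drug.

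This should be fixed, but it is not a fatal flaw. The relevant drugs are already recorded, section 11.2 bases the phase III decision on several endpoints, and a text change made before the data are analysed resolves it.

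**What to change.** The change concerns analysis scoring only and alters nothing about what may be given to patients.

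1. Bring 2.3, 7.1.1, 7.1.5, 11.1 and 11.3 to one cross-referenced rule.
2. In the 7.1.1 non-response definition, remove systemic steroids given for GVHD from the exempt items.
3. For scoring, limit the prophylaxis exemption to continuation, adjustment to drug level, or substitution with a recorded toxicity reason. Other additions, resumptions or escalations after day 0 score as non-response on day 28. The default then no longer depends on the unblinded investigator calling the drug GVHD therapy.
4. Pre-specify a sensitivity analysis in which every new, resumed or escalated systemic immunosuppressant after day 0 is non-response whatever its label. Systemic steroids for other indications can be handled there.
5. Use the same wording where 7.1.3 refers to additional lines of therapy.

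The cost is a few sentences, one field for the reason for change, and one extra analysis. The observed response rate may be slightly lower. For example, if two percentage points of an assumed 67% came from such patients, single-look power with success at 44 or more would fall from 0.807 to 0.695. That is a reason to settle the rule before the data are seen.
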